5.12.7.1. Treatment Emergent Anti-Insulin Lispro Antibody

The treatment-emergent anti-insulin lispro antibody (denoted as treatment-emergent antidrug antibody [TEADA] throughout this SAP) is based on the change from baseline (Visit 1) to post-baseline (post-Visit 1) in the anti-insulin lispro antibody level (percent binding). Treatment-emergent antidrug antibody can be subclassified as either treatment induced (not detected anti-insulin lispro antibody at baseline) or treatment boosted (detected anti-insulin antibody at baseline):

- treatment-induced response: change from not detected anti-insulin lispro at baseline (Visit 1) to postbaseline detected anti-insulin lispro
- treatment-boosted response: change from detected anti-insulin lispro at baseline (Visit 1) to postbaseline detected anti-insulin lispro antibody level (percent binding) at least 157% of the baseline value

The TEADA status will be determined using all data regardless of IP use. The number and percentage of patients with positive TEADA response any time during the treatment period will be summarized by treatment group. For patients with positive TEADA response any time during the treatment period, the number and percentage of patients with positive insulin cross-reactivity anytime during the treatment period, and the number and percentage of patients not meeting the TEADA criteria at Visit 15 (or last visit for patients who discontinue the study prior to Visit 15) will also be summarized by treatment group. Treatment groups will be compared by Fisher's exact test.

Both actual and change from baseline for the anti-insulin lispro antibody level in percent binding regardless of IP use will be summarized by scheduled visit prespecified in the protocol for patients with positive TEADA response anytime during the treatment period. The repeated measurement from Visit 1 to Visit 15 will be analyzed by an MMRM model with treatment, baseline value of the response variable, visit, and visit by treatment interaction as fixed factors and patient as the random factor. The ANCOVA model using treatment and baseline value as covariates will be used for the analysis of last nonmissing observation prior to or at Visit 15 and the analysis of maximum percent binding during the treatment period.

A listing of anti-insulin lispro antibodies at each visit will be provided for the safety population. The listing will include anti-insulin lispro antibody status (detected/not detected), anti-insulin lispro antibody percent binding, TEADA status (positive/negative), insulin cross-reactivity status, and insulin cross-reactivity percent binding.

Subgroup analysis for the following selected efficacy and safety variables will be performed by TEADA status during the treatment period:

- hemoglobin A1c and change from baseline in HbA1c
- basal, prandial, and total insulin dose
- treatment-emergent injection site reaction and hypersensitivity reactions

- event rate of all documented hypoglycemic events (based on the threshold of BG ≤ 70 mg/dL)

The analyses for HbA1c and change from baseline in HbA1c will be performed using an MMRM model for the primary analysis and the HbA1c data up to permanent discontinuation of IP. The model will include additional fixed terms of subgroup, subgroup by treatment interaction, subgroup by visit interaction, and 3-way interaction of treatment, subgroup, and visit.

The subgroup analysis for insulin dose will use the MMRM model specified in Section 5.11.5 using the efficacy estimands. The model will include additional fixed terms of subgroup, subgroup by treatment interaction, subgroup by visit interaction, and 3-way interaction of treatment, subgroup, and visit.

The incidence of treatment-emergent injection site reactions and hypersensitivity reactions will be analyzed by a logistic regression model including terms of treatment, subgroup, and treatment by subgroup interaction. All data regardless of IP use will be used for this analysis.

The negative binomial regression model specified in Table ITSB.5.4 with additional terms of subgroup, treatment by subgroup interaction will be used for the subgroup analysis of all documented hypoglycemia event rate while on IP.

The interaction effects (3-way for MMRM and 2-way for ANCOVA/negative binomial regression model) will be evaluated using a significance level of 0.10, unadjusted. If the interaction effect is significant ($p < 0.10$), separate analysis without the terms related with the subgroup will be performed for each subpopulation.

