CGM outcomes	All Randomized Patients with at least one from baseline and post-baseline observations	Visit 4	Visit 15
Basal, bolus, and total insulin doses, and bolus/total insulin dose ratios continuous analysis	All Randomized Patients	Last of Visits 3-4	Visits 5-15 prior to discontinuation of IP

Baseline and Postbaseline Definitions and Patient Population by Study Period and Type of Analysis

Study Period/Analysis	Patient Population	Baseline Observations	Post-Baseline Observations
7-point SMBG	All Randomized Patients with a baseline and at least one post-baseline observation	Visit 4 prior to initiation of IP	Visits 10 and 15 prior to discontinuation of IP
Health outcomes (PedsQL)	All Randomized Patients with a baseline and a post-baseline observation	Visit 4	Visits 15 prior to discontinuation of IP
Safety Laboratory Tests (chemistry, hematology) – continuous analysis	All Patients in the Safety Population with a baseline and a post-baseline observation	Last of Visits 1-4	Last of Visits 5-15 (planned including early discontinuation visits) regardless of IP use
Safety Laboratory Tests (chemistry, hematology) – categorical analysis	All Patients in the Safety Population with a normal baseline (with respect to the direction being analyzed) and a post-baseline observation	Last of Visits 1-4	Visits 5-15 (including unplanned visits) regardless of IP use
Hypoglycemia events	Safety Population	All Visits 2-4	All Visits 5-15 prior to discontinuation of IP
Weight and vital signs	All Patients in the Safety Population with a baseline and a post-baseline observation	Last of Visits 1-4	Visits 7, 10, 12, 15 prior to discontinuation of IP
Anti-insulin lispro antibodies	Safety Population	Visit 4	Visits 7, 10, 15 regardless of IP use
TEAE	Safety Population	Prior to first dose of randomized IP (or v4 date if missing), after first dose of open label Humalog (or v2 date if missing)	From randomization to Week 26 prior to discontinuation of IP OR from randomization to safety follow-up

Abbreviations: ANCOVA = analysis of covariance; HbA1c = hemoglobin A1c; IP = investigational product; ITT = intention-to-treat; MMRM = mixed-effect repeated measures model; PedsQL = Pediatric Quality-of-Life; SMBG = self-monitored blood glucose; TEAE = treatment-emergent adverse event.

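### SAP 5.12.7.1 does not name the population for the antibody-level models; read in sequence, they compare arms only among TEADA-positive patients

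*SAP*

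**What the plan says.** SAP 5.12.7.1 covers incidence and level.

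- **Incidence.** "The number and percentage of patients with positive TEADA response any time during the treatment period will be summarized by treatment group", with Fisher's exact test between arms. This carries no restriction to positives.
- **Level, summary.** Actual and change-from-baseline percent binding "will be summarized by scheduled visit prespecified in the protocol for patients with positive TEADA response anytime during the treatment period".
- **Level, models.** The next sentence reads "The repeated measurement from Visit 1 to Visit 15 will be analyzed by an MMRM model", with treatment, baseline, visit and visit-by-treatment terms. Then: "The ANCOVA model using treatment and baseline value as covariates will be used for the analysis of last nonmissing observation", and also for the maximum percent binding. Neither sentence names a population.

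A patient is TEADA-positive in one of two ways: "treatment-induced response: change from not detected anti-insulin lispro at baseline (Visit 1) to postbaseline detected anti-insulin lispro", or, if antibody was detected at baseline, a later percent binding "at least 157% of the baseline value".

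Elsewhere, SAP 5.1 makes the Safety Population the default for safety analyses, and SAP 5.12 lists these antibodies among the safety measures. The antibody row of Table ITSB.5.2 gives the Safety Population, baseline Visit 4, and post-baseline "Visits 7, 10, 15 regardless of IP use". SAP 5.12.7 and 5.12.7.1 put the antibody baseline at Visit 1.

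**The concern.** The phrase about the repeated measurement most naturally points back to the data of the sentence before it, which are those of TEADA-positive patients. On that reading both models estimate a treatment difference in a subgroup formed after randomization. Treatment can change who enters the subgroup, and entry depends on a rise in the very variable that is then compared. Adjusting for baseline percent binding does not restore comparability.

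At stake is the only between-arm analysis of antibody level that the documents describe. If one product raised antibody levels, the selected comparison could show little or no difference, because the arm with the higher levels also brings more patients just over the threshold, and these pull its mean down.

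**Working it through.** **Inputs from the documents.** The threshold for a boosted response is 157% of baseline, so ln(1.57) = 0.451 on the log scale. Planned arm sizes (Protocol 10.1) are 240/0.85 = 282.4, rounded up to 283, per blinded arm, and 120/0.85 = 141.2, rounded up to 142, in the open-label arm; 283 + 283 + 142 = 708, as stated. There is no TEADA rate, level, SD or power for antibodies, so there is no plan figure to reproduce. All antibody inputs below are assumptions.

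**Step 1: sign reversal by arithmetic.** Arm A has 20% positives with mean change 20. Arm B has the same 20% plus a further 10% with change 5. Everyone else has change 0.

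- All patients: A 0.20 × 20 = 4.0; B 0.20 × 20 + 0.10 × 5 = 4.5. B is higher.
- Positives only: A 20; B 4.5/0.30 = 15. B looks lower.

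In this simplified setting, any extra group with a change between 0 and 20 raises B's mean over all patients and lowers it among positives.

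**Step 2: masking of a uniform rise.** Let the log change be normal with SD 0.5 (assumed) and select values of at least 0.451. With k = (0.451 − μ)/0.5, the mean among positives is μ + 0.5 × φ(k)/(1 − Φ(k)).

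- μ = 0: 18.3% positive, mean among positives 0.724.
- μ = 0.2: 30.8% positive, mean among positives 0.771.

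A true difference of 0.20 shrinks to about 0.05.

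**Step 3: simulation with the SAP's TEADA rule.** There were 400 trials per scenario, 283 per arm, three post-baseline visits, and an ANCOVA of Visit 15 log change on treatment and baseline. Assumed: half of patients have detectable antibody at baseline; 20% in each arm are strong responders (mean log rise 1.2); a weak responder has mean log rise 0.6 and is drawn from the other patients of the test arm.

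| Test-arm effect | Positive, control / test | Difference, all | Difference, positives | Rejection, all / positives |
|---|---|---|---|---|
| None | 28.4% / 28.5% | 0.002 | 0.005 | 3.8% / 3.5% |
| Uniform +0.2 | 28.6% / 40.2% | +0.200 | −0.010 | 96.2% / 6.8% |
| Uniform +0.4 | 28.1% / 55.6% | +0.400 | −0.012 | 100% / 4.8% |
| Weak rise in 20% | 28.6% / 36.8% | +0.095 | −0.040 | 41.0% / 8.2% |
| Weak rise in 40% | 28.1% / 45.1% | +0.193 | −0.066 | 96.5% / 15.8% |
| Weak rise in 60% | 28.3% / 53.3% | +0.291 | −0.076 | 100% / 21.8% |

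In the 40% scenario the estimate among positives had the wrong sign in 81% of trials and was significant in the wrong direction in about 16%; over all patients the sign was never wrong. With 142 in the test arm the differences were +0.189 and −0.065, with the wrong sign in 79%. On raw percent binding the 40% scenario gave +1.04 over all patients and −0.99 among positives.

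**Step 4: size of the subgroup.** If 10% to 50% became positive (assumed), the level models would rest on about 28 to 142 patients per blinded arm and 14 to 71 in the open-label arm.

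**The case against.** The strongest answer is that the restriction is written for the summary and not for the models. Where the section means positives it says so, as in "For patients with positive TEADA response any time during the treatment period" for the cross-reactivity percentages. A model sentence with no population would then fall under the Safety Population default of SAP 5.1, which Table ITSB.5.2 repeats for antibodies. On that reading the models already use the right patients. This stands as far as it goes: a reader might infer that the SAP has chosen to compare levels only among positives, and the documents do not establish that. But Table ITSB.5.2 does not settle the matter either, since the same row disagrees with the text on the baseline visit.

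A reader might also infer that p-values among positives would mean nothing. That is too strong. With no treatment effect the selected comparison rejected in 3.5% of simulated trials, so it was not biased there. The fault is that, when treatment affects positivity, the contrast is not the effect on level in the randomized arms.

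Finally, a reader might infer that the trial's immunogenicity result would be reversed. The documents do not support that. Reversal needs an excess of mainly weak responders, which is an assumption. The unrestricted incidence comparison would also show the excess: in Step 1, 30% against 20%. Incidence is the only antibody endpoint among the objectives (objective 12, exploratory), Protocol 10.3.6 specifies no between-arm model of level, and a Safety Population listing is planned as well.

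**Conclusion.** The point holds as an unstated analysis population with a real consequence under its most natural reading. If the MMRM and ANCOVA are run in TEADA-positive patients, they condition on a post-randomization status defined by the outcome. They can then hide a uniform increase in antibody level (in the simulation, +0.20 became −0.01 and rejection fell from 96% to 7%), and can change its sign if one product adds mainly weak responders (+0.19 became −0.07). These sizes rest wholly on assumed antibody distributions and show what can happen, not what to expect in this trial. If the models are run in the Safety Population, the problem does not arise, but the SAP should say so. Severity is minor: level is not a listed endpoint, and the HbA1c results and the incidence comparison are unaffected.

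**What to change.** In SAP 5.12.7.1, state that the MMRM and ANCOVA of percent binding include all Safety Population patients with a baseline and at least one post-baseline value, regardless of TEADA status. Keep the by-visit summary in TEADA-positive patients as descriptive, without between-arm p-values. In the same edit, reconcile the antibody baseline (Visit 4 in Table ITSB.5.2, Visit 1 in 5.12.7 and 5.12.7.1). Also list the response visits of the MMRM: its stated span starts at Visit 1, so with a Visit 1 baseline the same value would be both response and covariate.

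The cost is SAP wording and minor reprogramming. No new data are needed, because the Schedule of Activities already has antibody samples at Visits 1, 4, 7, 10, 15 and early discontinuation.

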**7.2.1.2.2. Prandial Insulin Adjustment**

Prandial insulin should be titrated during the treatment period in order to reach optimal dosing and achieve glucose targets. Reasonable efforts should be made to achieve these targets during the first 12 weeks, however prandial insulin dose adjustments may continue throughout the treatment period in order to achieve or maintain glycemic targets or for safety reasons such as hypoglycemia or unacceptable hyperglycemia. The prescribed prandial insulin dose is determined by, and the responsibility of, the investigator in consultation with the patient or caregiver. Modifications in the calculation of the insulin dose may be influenced by other clinical circumstances and safety considerations known to the investigator.

Additional postprandial glucose monitoring may be considered during the days following transition to study insulin at the discretion of the investigator. Patients may use their usual correction factor (CF) or insulin sensitivity factor (ISF) to determine dose needed to correct a high BG to their target level. This may be in addition to their meal-related dose. Investigators should instruct patients and caregivers of the potential for hypoglycemia if prandial insulin is given too frequently to a previous IP injection (insulin stacking).

Patients may determine their prandial IP dose by pattern adjustment or carbohydrate counting, but they should maintain the same dosing method throughout the study.

- Pattern adjustment: The patient is prescribed a fixed dose or dose range of insulin for each meal. The fixed insulin dose may be individualized for each meal.
- Carbohydrate counting: The patient performs carbohydrate counting for prandial insulin dosing; prandial insulin dose is based upon the estimated carbohydrate content of the meal (as unit of insulin per grams carbohydrate).

Based on the patient's individual needs and glucose values, the insulin to carbohydrate ratio and CF should be assessed and adjusted as often as needed in order to meet the target glucose values described in [Table ITSB.4](#). Postprandial SMBG values from 7-point SMBG profiles should also be evaluated for optimization of prandial insulin dosing.

For patients who are using pattern adjustment, the prandial insulin dose should be assessed and adjusted as often as needed in order to achieve glucose targets.

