### **10.3.7. Other Analyses**

#### **10.3.7.1. Subgroup Analyses**

The following subgroups will be analyzed using the efficacy estimand to evaluate consistency of treatment effects on the primary efficacy measure if there are sufficient numbers of patients in each treatment by subgroup (for example, 10%):

- Age (Age Group 1: 1 to <12, 12 to <18 years and Age Group 2: 1 to <6, 6 to <12, 12 to <18 years)
- HbA1c stratum ( $\leq 8.0\%$ ,  $> 8.0\%$ )
- Type of basal insulin at randomization (insulin glargine, detemir, or degludec)
- Sex (male or female)
- BMI ( $< 25$ ,  $\geq 25$  kg/m^2 and  $< 30$ ,  $\geq 30$  kg/m^2)
- Duration of diabetes (using the median as the cutoff)
- Race
- Ethnicity
- Country
- Region
- Prandial insulin dosing plan (carbohydrate counting, pattern adjustment).

Analyses for HbA1c and change from baseline in HbA1c will be performed using an MMRM model that includes the same fixed effects given for the primary analysis model plus factors of subgroup, 2-way interaction of subgroup and treatment, 2-way interaction of subgroup and visit, and 3-way interaction of treatment, visit, and subgroup. The interaction of subgroup and treatment at the primary endpoint (Week 26) will be evaluated to assess the treatment by subgroup interaction.

Additional subgroup analyses may also be performed.

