5.13. Subgroup Analyses

5.13.1. Subgroup Analyses for HbA1c

The following subgroups will be analyzed for HbA1c if there are sufficient numbers of patients per group (eg, at least 10% in each group) for both the ITT and efficacy estimands:

- age (age group 1: 1 to <12 versus 12 to <18 years and age group 2: 1 to <6, 6 to <12, and 12 to <18 years)
- Body Mass Index (BMI, < 25 kg/m², ≥ 25 kg/m² and < 30 kg/m², ≥ 30 kg/m²)
- hemoglobin A1c stratum ($\leq 8.0\%$ versus $> 8.0\%$)

- sex (male versus female)
- duration of diabetes (using the median as the cut-off)
- race
- ethnicity
- country
- region
- type of basal insulin (glargine, degludec and detemir)
- prandial insulin dosing plan (carbohydrate counting or pattern adjustment)
- personal continuous glucose monitoring (CGM) or flash glucose monitoring (FGM) use (yes, no)

For the ITT estimand, analyses for HbA1c and change from baseline in HbA1c will be performed using an ANCOVA model that includes the same fixed effects and baseline as a covariate given for the primary analysis model plus factors of subgroup and 2-way interaction of subgroup and treatment.

For the efficacy estimand, analyses for HbA1c and change from baseline in HbA1c will be performed using an MMRM model that includes the same fixed effects given for the primary analysis model plus factors of subgroup, 2-way interaction of subgroup and treatment, 2-way interaction of subgroup and visit, and 3-way interaction of treatment, visit, and subgroup. The interaction of subgroup and treatment at the primary endpoint will be evaluated to assess the treatment by subgroup interaction.

The subgroup interaction effect will be evaluated using a significance level of 0.10, unadjusted.

Additional subgroup analyses may also be performed.

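### SAP 5.12.7.1 judges antibody effect modification in the MMRMs by a test of change across visits, not by the Week 26 interaction; separately, SAP 5.1 sets interaction tests at 0.05 against the protocol's 0.10

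*SAP*

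**What the plan says.** SAP 5.12.7.1 extends the primary HbA1c MMRM and the insulin-dose MMRM with TEADA status, its two-way interactions with treatment and with visit, and the three-way term. The rule for judging effect modification is: "The interaction effects (3-way for MMRM and 2-way for ANCOVA/negative binomial regression model) will be evaluated using a significance level of 0.10, unadjusted". If the result is below 0.10, then "separate analysis without the terms related with the subgroup will be performed for each subpopulation". Injection site and hypersensitivity reactions "will be analyzed by a logistic regression model including terms of treatment, subgroup, and treatment by subgroup interaction".

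For the other HbA1c subgroups, SAP 5.13.1 adds the same kinds of term to the MMRM but names a different test: "The interaction of subgroup and treatment at the primary endpoint will be evaluated to assess the treatment by subgroup interaction". Its level is also 0.10: "The subgroup interaction effect will be evaluated using a significance level of 0.10, unadjusted". Protocol 10.3.7.1 agrees and names the visit: "The interaction of subgroup and treatment at the primary endpoint (Week 26) will be evaluated to assess the treatment by subgroup interaction".

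On the general level for treatment-interaction tests, protocol 10.3.1 gives two-sided 0.10 and SAP 5.1 gives two-sided 0.05. SAP 5.13.2 (hypoglycemia subgroups) relies on the two-way interaction and states no level.

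**The concern.** A three-way term with visit answers the question of whether the antibody-related difference in treatment effect varies over time. The clinical question is whether antibodies modify the treatment effect at all. The two coincide only when the modification changes over the visits analyzed. If antibodies blunt the effect on HbA1c by the same amount at Weeks 6, 12 and 26, the three-way term is null by construction, and the separate fits by TEADA status follow only by chance. The SAP does not explain why TEADA is handled differently from every other HbA1c subgroup.

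The level conflict is a separate matter. It does not touch the TEADA tests, which carry their own 0.10. It leaves the hypoglycemia subgroup interactions at 0.05 under the SAP and 0.10 under the protocol.

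**Working it through.** **Inputs from the documents.** SD 1.1% and 240/240/120 completers (protocol 10.1). HbA1c MMRM at Visits 7, 10 and 15, that is Weeks 6, 12 and 26; insulin dose at Visits 5 to 15, that is 11 visits (SAP Table ITSB.5.2; protocol Schedule of Activities). Level 0.10.

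**Assumptions not in the documents.** 30% TEADA positive (range 10 to 50%); between-visit correlation ρ of 0.5 to 0.8 with compound symmetry; an interaction of up to 0.4% HbA1c, equal in both LY900014 arms.

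**1. The plan's own power figures.** None is given for a TEADA test. Those in protocol 10.1 reproduce:
- 240 vs 240: SE = 1.1 × √(2/240) = 0.1004. Φ(0.4/0.1004 − 1.96) = 97.8% (stated: above 95%). With margin 0.3, 84.8% (stated: above 80%).
- 240 vs 120: SE = 1.1 × √(1/240 + 1/120) = 0.1230. Φ(0.33/0.1230 − 1.96) = 76.5% (stated: about 76%).

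**2. Formulas.** Let δ_t be the treatment-by-TEADA interaction at visit t. For each arm let v = 1/n₊ + 1/n₋. With equal interactions in the two LY900014 arms,

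K = 1 / [v_Humalog + 1/(1/v_LY900014 + 1/v_LY900014+20)].

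At 30% positive, v = 1/72 + 1/168 = 0.01984 for each 240-patient arm and 1/36 + 1/84 = 0.03968 for the 120-patient arm. So K = 1/(0.01984 + 1/(50.4 + 25.2)) = 30.24.

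- 3-way test: noncentrality = K × Σ(δ_t − mean δ)² / [SD² × (1 − ρ)], with (3−1)(2−1)(3−1) = 4 df.
- Week 26 test: noncentrality = K × δ₂₆² / SD², with 2 df.

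**3. Constant interaction.** Every δ_t equals the mean, so the 3-way noncentrality is 0 and the test rejects 10% of the time. This holds for any effect size, TEADA share, correlation or number of visits. For the Week 26 test, 30.24 × 0.16/1.21 = 4.00, which gives 54%. At 10%, 20%, 30% and 50% positive, K is 12.96, 23.04, 30.24 and 36.00, and power is 30%, 45%, 54% and 61%.

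A simulation (20,000 trials per setting, estimated unstructured covariance, 50% positive, ρ = 0.7) agrees. For constant interactions of 0, 0.5% and 1.0%, the 3-way test rejected 10.3%, 10.2% and 10.0% of the time, and the Week 26 test 9.9%, 77.9% and 99.96%.

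**4. Other time profiles for HbA1c** (30% positive, ρ from 0.5 to 0.8):

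| Interaction at Weeks 6/12/26 | Σ(δ_t − mean)² | 3-way test | Week 26 test |
|---|---|---|---|
| 0.4/0.4/0.4 | 0 | 10% | 54% |
| 0.2/0.4/0.4 | 0.0267 | 21–39% | 54% |
| 0/0.2/0.4 | 0.0800 | 44–81% | 54% |
| 0.4/0.4/0 | 0.1067 | 55–91% | 10% |

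Example, growing effect at ρ = 0.5: 30.24 × 0.0800/(1.21 × 0.5) = 4.00 on 4 df, which gives 44%.

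**5. Insulin dose.** There are 11 visits, so (3−1)(2−1)(11−1) = 20 df. The effect is set to the same standardized size, 0.4/1.1 = 0.36 SD.
- Constant: 10% for the 3-way test, 54% for Week 26.
- Rising to Week 12, then flat: 43–84% for the 3-way test under compound symmetry. Under first-order autoregressive errors it is 18% at adjacent-visit correlation 0.5 and 36% at 0.95. The Week 26 figure is 54% throughout.

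**6. Level conflict.** SAP 5.13.2 has 7 groupings (two age splits, HbA1c stratum, region, basal insulin, dosing plan, personal CGM/FGM use), each for rate and incidence: 14 tests per period. Expected false flags are 14 × 0.05 = 0.7 or 14 × 0.10 = 1.4.

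**The case against.** **Little hangs on the trigger.** The TEADA subgroup model is fitted in any case, and SAP 5.1 has model-based treatment differences displayed. A reader might infer that a steady antibody effect would go unexamined. The documents do not support that: only the extra separate fits depend on the p-value. TEADA status also arises after randomization, and the analysis is exploratory. All of this stands and limits the weight of the point.

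**The better test depends on the time course.** Antibodies may be transient: the SAP itself counts "the number and percentage of patients not meeting the TEADA criteria at Visit 15" among patients who were TEADA positive. A dose effect may build up, since the protocol says "Reasonable efforts should be made to achieve these targets during the first 12 weeks". A dose interaction at full size from Week 2 would also precede the first post-randomization antibody sample at Week 6. So it would be wrong to infer that the 3-way test is generally inferior; for an effect gone by Week 26 it is the Week 26 test that has no power. Nor does the 3-way test reliably win for late-building effects: at ρ = 0.5 it has 44% against 54% for HbA1c, and for dose the result turns on the error structure. For a constant effect, averaging over visits would beat Week 26 (60–70% against 54%), but Week 26 is the timepoint that the plan already uses.

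**The sentence might cover a visit-specific contrast.** This is possible, but SAP 5.13.1 uses different words when it means the primary endpoint, so the overall 3-way test is the natural reading.

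**The 0.05 looks like an oversight.** The SAP revision history points to 0.10 as the intended level for subgroup interactions. A reader might infer a deliberate, unjustified departure from the protocol, but an un-updated sentence is more likely, and SAP 5.1 lets a justification appear in the study report. The conflict between the current texts remains.

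**ANCOVA in the level sentence.** No TEADA subgroup analysis listed there uses ANCOVA; logistic regression is evidently meant. One should not infer that the logistic model lacks a level. The slip is clerical.

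**Conclusion.** The concern holds in two limited parts.

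First, the MMRM decision rule in SAP 5.12.7.1 cannot detect a treatment-by-TEADA interaction that is constant over visits beyond its 10% false-positive rate. That is algebra and needs no assumption. The comparison with about 54% for the Week 26 contrast rests on the assumed 0.4% interaction and 30% TEADA share, and ranges from 30% to 61% as the share goes from 10% to 50%. For effects that grow or fade, the ranking depends on the assumed profile and correlation. The main reasons to change are that the rule does not ask the question of interest and that it differs, without explanation, from the test the plan uses for the other HbA1c subgroups.

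Second, SAP 5.1 contradicts protocol 10.3.1 and SAP 5.12.7.1 and 5.13.1 on the interaction level, and by default governs SAP 5.13.2. No follow-up action is attached to a flag there, so the consequence is in how interactions are labelled.

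Neither part affects the primary HbA1c comparison or the two HbA1c tests that follow it in sequence.

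**What to change.** 1. In SAP 5.12.7.1, make the treatment-by-TEADA interaction at Week 26, from the MMRM already specified and at 0.10, the test and the trigger for HbA1c and insulin dose. Report the 3-way term as supportive.
2. In SAP 5.1, change the interaction level from 0.05 to 0.10. This restores the protocol's level and covers SAP 5.13.2.
3. As a clerical edit, replace ANCOVA with logistic regression in the level sentence of SAP 5.12.7.1.

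The cost is three short text edits and one contrast from models that will be fitted anyway, with no new data. The false-trigger rate stays at 10% per endpoint. The downside is less sensitivity to an effect that fades by Week 26, which is why the 3-way result should still be shown. In SAP 5.13.2, expected false flags become 1.4 rather than 0.7 per period, as the protocol's level already implies.

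Letting either test trigger the separate fits would cover more profiles. But it would raise the false-trigger rate from 10% to about 18–19% on each of four endpoints (HbA1c and basal, prandial and total dose) and goes beyond what SAP 5.13.1 does, so it is not recommended.
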